# Pre-Trial Part

## Title

Mentalization-based Mental Health Education  
in a naturalistic patient population  
from a psychiatric out-patient clinic in North Norway:  
A randomized controlled study.

---

## 1b Abstract

To be written in the scientific article following the trial.

## Introduction

---

### 2a Background

Mentalizing (Mz) is a psychodynamic concept which captures our ability to recognize and think about ones own and other peoples thoughts and feelings. Mentalizing is related to a wide range of other scientifically and historically rooted concepts such as: Metacognition, reflective function, executive function, theory of mind, externalization, self-control, self-consciousness and thoughtfulness. Mentalizing has fundamental significance for mental & social functioning (Fonagy 2002, Liotti 2011).

Intensive Mentalization-Based Therapy/Training (MBT) for Borderline Personality Disorder (BPD) has shown very promising long-term results (Batemann 2008). That has stimulated a wider interest into this treatment approach.

This fundamental approach - to teach and practice thinking - especially how to think carefully in critical situations, we consider to be in line with the field of **P**-factor theory and research (Caspi 2018) which indicates that severe **P**psychopathology in general is rooted in fundamental neurobiological vulnerability of thinking - often caused by genetics and trauma - that is compromised mentalizing.

P-factor and Mz theory and research set a perspective for a wider application - that is efficient mental health promotion and prevention of mental health disease on a public health level - which also has been called for for health economic reasons (Kadzin 2011, Roth 2006).

## Mz CONSORT Protocol

We responded to this call 15 years ago by developing an Mz-based Mental Health Education Program which has since been tested in various public health domains & countries.

Our Mz program focus on how we as humans can use *the strongest tools in the world - our Thoughts* - to protect ourself and each other and boost mental repair - especially when life is hard. It is not *Psychoeducation* about the characteristics of specific disorders/symptoms - it is Mental Health Education in daily language - how to reinforce our basic common life toll - *thoughts* - in order to cope with life challenges (references on [www.thoughtful.house/science](http://www.thoughtful.house/science)).

The program is designed to optimize personal (user-driven) meaningfulness and has been tested during 15 years in several countries. Results fra Denmark, Greenland and Italy indicate that the program can help to reduce conflicts, stress and sick leave and support mentalizing & learning in different populations (Bak 2015, Lundgaard Bak 2018, Lundgaard 2021, Valle 2016).

Based on these experiences and results, we have in 2020-2021 developed a new, expanded and more user friendly version - called *Thoughtful* - as a web-based self-treatment program which can be found on [www.tenksom.house](http://www.tenksom.house) (Norwegian), [www.thoughtful.house](http://www.thoughtful.house) (English) and [www.omtanke.house](http://www.omtanke.house) (Danish). Greenlandic and Italian versions are expected to be published in 2023.

The Thoughtful/Mz program approach is developed in line with decades of evidence on a meta-analytical level about the efficiency of patient education for somatic and mental disorders - that is a *general recovery approach*.

For transparency the program has a science theme in which comprehensive theory and research behind and about the program on [www.thoughtful.house/science](http://www.thoughtful.house/science) - including our E-book *Thoughts behind Thoughtful - Theory & Research*.

In Appendix 2 in this protocol you will find a short introduction to the Thoughtful program.

The Thoughtful program is a supplemental effort to any other measures aiming to support peoples life skills - in any life domain. It is a self-directed program which means that it can be introduced with a minimum of ressources within any organization.

---

## 2b Objectives

The objective of the current naturalistic/pragmatic randomized study is to test the feasibility and efficiency of the Thoughtful program in an unselected waiting list patient population from a psychiatric out-patient clinic in the University Hospital of North Norway.

## Methods

---

### 3a Trial Design

This is a randomized clinical trial in which individual waiting list patients are allocated 1:1 into intervention group and control group.

---

### 3b Changes to methods after trial commencement

NONE.

---

### 4a Participants

All norwegian speaking patients on the outpatient clinic waiting list are considered eligible for the study. Thus no patients will be a priori excluded from the study population for any clinical reason - for instance diagnosis, co-morbidity, symptom severity or use of medicine or other kinds of treatment.

So this is an intention-to-treat & naturalistic/pragmatic trial design.

No patients will be excluded from *treatment as usual* because of the trial.

---

### 4b Settings

The outpatient clinic is a part of a general District Psychiatric Centre in North Norway (Harstad). The clinic is serving a population of 31.300 citizens (mixed rural & small city population in 4 municipalities: Harstad, Lødingen, Sjølsund & Kvarfjord). The centre also has an inpatient ward and an emergency team.

The centre treats all categories of psychiatric disorders with a broad range of psychoterapeutic, medical and somatic assessments and measures.

Because this is a naturalistic/pragmatic study the patient population will be a mix with respect to socio-demographic and psychopathological parameters - and with respect to length of waiting period & previous treatment measures.

According to The World Bank & OECD Norway is one of the richest countries in the world with low social inequality.

Relevant data for the study are collected from the electronic patient record system and a separate research survey database.

---

## 5 Intervention

Based on the theories and research mentioned above *patients in the intervention group* will be invited to join a group-based 6 hour *Thoughtful* course (8 patients per group). *Two delivery models will be tested:*

- A: 2 hour session per day - 3 days in a row in one week.
- B: 1 day 6 hour course.

Audios from the web-program and an illustrated book with core concepts & themes are demonstrated. Everything lectured can be reviewed at home by participants in greater details in the Audios and the book.

In group A patients are offered an individual session 1 month after the course.  
Group B patients are offered individual session when needed.

The course has been approved by the University Hospital as a documented treatment equated with other standard treatments.

The *Thoughtful* course is an *educational* course where participants are offered research-based knowledge in daily language about thinking. So patients can participate without telling anything about their personal challenges - just be present - anonymous - listen - and think. Naturally they are welcome to tell and ask - but it is not a requirement. In the hour immediately after each session participants are offered a short individual talk if needed. Pilot experiences show that participants are comfortable with this approach.

All patients enrolled in the trial - in the intervention group and in the control group - will keep their position on the waiting list and will have access to individual assessment and treatment as usual. So the *Thoughtful* intervention is a *supplemental* effort which does not affect standard procedures or patient legal rights.

Patients who are not able to join the group course because of social anxiety or practical reasons will be given course materials for self study and they will be offered individual introduction.

This delivery model has several advantages:

- In the *Thoughtful* program knowledge is presented in an illustrated book and in sound files (Audios) which makes it possible for people who don't read to join anyway. People who don't want to talk about their thoughts and feelings - who are not comfortable about sharing their burdens with others - can also join - that is self-treatment.
- Patients with for instance social anxiety and/or low mental energy level who have difficulties joining standard talking-therapy will in this way have access in a home setting to research-based self-treatment knowledge and training-tools. They can repeat the lectures any number of times and at times which suits them best. They can study alone or in companion with relatives or friends who support them.

- High fidelity is inherent in this kind of program as the material presented in book and audio files remains the same no matter how many times it is used and it is independent of variations in therapist approaches. The content of the intervention can be shared widely exactly as tested in randomized control trials.
- *Thoughtful* is a modular user-driven program. Research indicates that modular user-driven programs may have double clinical efficacy compared with standard delivery models (Weisz 2012).
- Research indicates that self-help materials supplemented by professional guidance may reduce symptoms in comparison to waiting list or control treatment and may produce comparable outcomes to formal therapist-delivered psychological therapies. Self-help concepts may thus have utility as a first step in treatment (Perkins 2009).

In the current trial the web-based program is combined with options for direct professional contact. Thus the individual patient can tailor the intervention to his/her own needs and circumstances.

---

## 6a Outcomes

Primary outcome will be *use of mental health hospital services* measured by the number of contact/treatment days to the centre (in-patient, out-patient and emergency team contacts) in a 12 month follow up period from the day of intervention start. This outcome measure is considered to have a high face validity and to be a reliable proxy measure for patient wellbeing when applied within a consistent organizational context (Burns 2007, Addington 2012).

Secondary outcomes will be:

- Average change in score *before and 6 months after* intervention on a 3 item anonymous mental wellbeing questionnaire - see Appendix 1.
- Medication level based on pharmacy data.

The use of standard patient record data as outcome measures is in line with the Recommendation on Criteria for Establishing Strong Evidence of Effectiveness from a National Academies Report (O'Connell 2009).

A trial group sample of participants will be interviewed for a qualitative research study.

---

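### Section 6a does not exclude delivery of the intervention from the primary outcome: each attender gains 3 to 4 days in A, at least 1 in B, and controls none, against a planned effect of about 0.6 day

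*Protocol*

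**What the plan says.** Section 6a counts "the number of contact/treatment days to the centre (in-patient, out-patient and emergency team contacts"), and counts them "in a 12 month follow up period from the day of intervention start". It defends this count as "a reliable proxy measure for patient wellbeing".

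Section 5 describes two delivery models: A is a "2 hour session per day - 3 days in a row in one week" and B is a "1 day 6 hour course". On individual sessions it says "In group A patients are offered an individual session 1 month after the course" and "Group B patients are offered individual session when needed". Patients who cannot join the group are offered an individual introduction. The course is supplementary to usual care, which both arms keep. On its status, section 5 states: "The course has been approved by the University Hospital as a documented treatment equated with other standard treatments".

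Three other places bear on the point. Section 11a says that each patient's treatment has to be documented in the patient record. Data protection says that the administrative data come, anonymised, from the hospital's record system. Section 7a plans for a 5% reduction from 1250 contact days per 100 patients and sets up separate comparisons of 64 against 64 for A and for B. No section says whether course days or programme sessions enter the primary count.

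**The concern.** The window opens on the day the intervention starts, so the course falls inside it. A hospital-approved treatment, given by the clinic on top of usual care, is on a plain reading a contact/treatment day. Patients in the intervention arm then collect days simply by receiving what they were allocated, and controls have no matching days. Attending an assigned course says nothing about wellbeing, which is what section 6a wants the count to stand for.

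Three things are at stake. The difference between arms is pushed upwards, against the intervention, so a real reduction in other contacts could be hidden or appear as an increase. The push is larger in A than B's minimum, so the two comparisons in 7a, and the analysis by delivery group foreseen in section 12 (Subgroup analyses), would not be on the same footing. And the 5% in 7a has two quite different meanings, depending on whether delivery days are in it.

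**Working it through.** **Inputs**
- Baseline (7a): 1250 days per 100 patients, so 1250/100 = 12.5 days per patient per year.
- Planned reduction (7a): 5%.
- SD 100 days (unit not given), type 1 error 5% (taken as two-sided), power 0.80, 64 per group (7a).
- Delivery days per attender, d (section 5): A 3, or 4 with the one-month session; B 1 as a minimum, because individual sessions on need can add more; controls 0. The short talks after sessions fall on course days and add none.
- Uptake, u: not stated. The values 50% and 100% below are assumptions.

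**The plan's own figures.** Planned effect: 0.05 × 12.5 = 0.625 day per patient. With n = 2(z₀.₉₇₅ + z₀.₈₀)²(SD/effect)², an effect of 0.625 and SD of 100 give about 401,900 per group; 62.5 and 100, both per 100 patients, give 41. The stated 64 corresponds to an effect of 0.50 SD, so it does not follow from the stated inputs. That is a separate defect of 7a. The steps below up to the last use only the 12.5 and the 5%.

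**Delivery days relative to the planned effect.** 3/0.625 = 4.8 and 4/0.625 = 6.4 in A; 1/0.625 = 1.6 or more in B. These ratios do not depend on the SD.

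**Reading 1: the 5% refers to contacts other than delivery.** The effect is cancelled when d × u = 0.625, that is, at u = 0.625/d.

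**Reading 2: the 5% is net of delivery days.** Other contacts must then fall by (0.625 + d × u)/12.5.

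| | A, d = 3 | A, d = 4 | B, d = 1 (minimum) |
|---|---|---|---|
| Reading 1: difference between arms at full attendance, d − 0.625 | +2.375 | +3.375 | +0.375 or more |
| Reading 1: cancelling uptake | 20.8% | 15.6% | 62.5% or less |
| Reading 2: required fall, full attendance | 3.625/12.5 = 29% | 4.625/12.5 = 37% | 1.625/12.5 = 13% or more |
| Reading 2: required fall, 50% uptake | 2.125/12.5 = 17% | 2.625/12.5 = 21% | 1.125/12.5 = 9% or more |

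With A and B pooled equally and B at its minimum, the mean is 2 to 2.5 days. The cancelling uptake is 0.625/2.5 = 25% to 0.625/2 = 31%, and the required fall at full attendance is 2.625/12.5 = 21% to 3.125/12.5 = 25%. Individual introductions for patients outside the group are left out; including them would lower the cancelling uptakes.

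**Other baselines.** The 12.5 describes the whole centre in 2021 and not waiting-list patients, so half and double were tried.
- Baseline 6.25 (effect 0.3125): cancelling uptake 8-10% in A and at most 31% in B; required fall at full attendance 53-69% in A and at least 21% in B.
- Baseline 25 (effect 1.25): cancelling uptake 31-42% in A; in B a single course day never cancels the effect (1.25/1 exceeds 100%). Required fall 17-21% in A and at least 9% in B.

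**Size against sampling error.** If the SD of 100 days is per patient, the standard error with 64 per arm is 100 × √(2/64) = 17.7 days. Four days is 4/17.7 = 0.23 standard error, and 0.04 SD. The planned effect on that scale is 0.625/100 = 0.006 SD.

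**The case against.** The strongest reply is that the central step is inferred. Section 5 also calls the course educational and lets patients attend anonymously, and nowhere is it said that a group session is logged as an out-patient contact. Section 11a concerns documentation of treatment in general. This stands as a caveat: a reader might infer that the protocol declares course days part of the outcome, and it does not. What it does is define an all-inclusive count, open the window at the course, class the course as treatment and exclude nothing. If the days are in fact not registered, one sentence settles it.

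Second, total service use including delivery is a legitimate question in a pragmatic health-service trial. That is so, and it deserves reporting. But the outcome is justified as a stand-in for wellbeing, and if net use is meant, 7a's 5% implies a far larger fall in other contacts than it appears to.

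Third, the shift may look trivial, or enormous, depending on the SD. On the per-patient reading it would rarely decide a test. A reader might instead put the SD on the same per-100-patients scale as the 1250 and infer a shift of 1 to 4 SD. That needs a per-patient SD of 1 day around a mean of 12.5, when even a Poisson count would have √12.5 = 3.5, so it is not credible and is not relied on here.

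Fourth, which record codes enter a count is often left to a statistical analysis plan. Here, however, the protocol itself fixes the outcome in words that take these days in, and anonymised extraction may leave no way to separate them later.

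**Conclusion.** The point holds and should be fixed. Followed as worded, section 6a adds days to one arm only, for a reason unrelated to patients' condition, and in A those days are about five to six times the planned effect. The conclusion rests on course sessions being coded as contacts (likely, not stated), on the whole-centre baseline and on an unstated uptake. For A, the cancelling uptake stays at 8-42% from half to double that baseline. For B the result is less firm: one day is a minimum, and at double the baseline one day alone does not cancel the effect.

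Two stronger conclusions are not supported. A false finding of benefit cannot come from this, because the shift runs against the intervention. Nor do the documents show that the hypothesis test is badly distorted: with a per-patient SD of 100 days the harm is mainly to the estimate and its sign. A smaller SD would make the shift larger in standard errors, in proportion, but the protocol gives no other value.

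**What to change.** In 6a, define the primary outcome as contact/treatment days excluding delivery contacts that the protocol schedules: the group course days, the individual introduction that replaces the course, and the one-month individual session in A. A day still counts if a contact outside the programme took place on it. Set the flag from course dates and attendance lists before the data are anonymised.

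Keep on-demand individual sessions in the primary count, since they reflect need. Add sensitivity analyses that include, and that exclude, all programme individual sessions in both A and B, so that the two models can be compared under one rule.

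Report total days including every delivery contact as a secondary service-use outcome. In 7a, state whether the 5% includes delivery days.

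The cost is one or two sentences in 6a, one in 7a and the flag at extraction. The downsides are that delivery contacts must be identified reliably from attendance lists and that total service use becomes a secondary outcome.

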## 7a Sample size

The total number of contact/treatment days in the centre (out-patient clinic, inpatient ward and emergency team) in 2021 was 14.621 = 1250 contact days per 100 patients.

Based on a standard deviation of 100 days, Type 1 error level of 5%, a 5% expected reduction of total number of contact days per year in the intervention group, we will need 64 patients in the intervention group and 64 patients in the control group in order to obtain a statistical power of 0,80.

Currently around 300 patients are on waiting list. Prioritizing long waiting time we enroll and randomize 256 patients in the trial:

- 64 patients in trial group A (3-day course) & 64 patients in control group A.
- 64 patients in trial group B (1-day course) & 64 patients in control group B.

So we expect this to be a reliable study with acceptable statistical power.

---

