# Randomization

---

8a Sequence generation,

9 Allocation concealment mechanism

10 Implementation

During the trial period 64 waiting list patients per month in 4 months will be allocated.  
The patients are 1:1 computer randomized to trial/control group.

See also 11a.

---

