## Timeline

Patient enrollement is expected to start in march 2023 and continue for 4 months.

Follow up period is 1 year.

So data analysis is expected to start in july 2024.

---

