## Appendix 1: Questionnaire

Both Intervention and control group participants will be asked to answer 3 questions *anonymously* before intervention and 6 months later - via the University Research Department survey program Redcap.

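### The 12-month primary outcome window opens at the start of the intervention, a date that controls and invited patients who never start do not have, and the protocol gives no common index date

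*Protocol*

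**What the plan says.** The primary outcome in section 6a is the number of days of contact with the centre, counted "in a 12 month follow up period from the day of intervention start". Section 4a states the analysis principle: "So this is an intention-to-treat & naturalistic/pragmatic trial design".

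Under section 5, intervention patients are invited to a course in groups of eight. Both arms "will keep their position on the waiting list and will have access to individual assessment and treatment as usual". "Patients who are not able to join the group course because of social anxiety or practical reasons" receive self-study material and the offer of an individual introduction.

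Section 7a plans "64 patients in trial group A (3-day course) & 64 patients in control group A", and the same numbers for group B. The Randomization section adds: "During the trial period 64 waiting list patients per month in 4 months will be allocated".

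The Timeline gives four months of enrolment from March 2023 and one year of follow-up, without saying what starts the year: "So data analysis is expected to start in july 2024". Appendix 1 times the questionnaire, for both arms, "before intervention and 6 months later".

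**The concern.** Time zero for the primary outcome is an event that follows randomisation and happens in one arm. Controls have no intervention start. Invited patients who decline everything have none either. Those who take the self-study route may have one, but the protocol does not say whether it is the day the material is handed over, first used or introduced. An intention-to-treat count needs a window for all of these patients.

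Two things are at stake.

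- **Freedom to choose the window.** Section 11a accepts that neither patients nor therapists can be completely blinded, and the outcome comes from existing records. Without a written rule, the date from which controls and never-starters are counted could be settled with the data in hand.
- **Comparability of the arms.** Everyone stays on the waiting list, and section 7a gives priority to long waiters. Contact days may therefore depend on where the window lies relative to the end of the wait. Taken literally, section 6a also leaves out the intervention arm's contacts between randomisation and course, while controls' contacts in that interval might be counted. A difference could then arise without a treatment effect, or a real effect could be hidden.

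**Working it through.** **1. Is there a common index date anywhere in the protocol?**

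| Section | What it fixes | Date for controls and never-starters? |
|---|---|---|
| 4a | Intention-to-treat | No |
| 5 | Invitation, self-study route, usual care in both arms | No |
| 6a | 12 months from intervention start | No |
| 7a | Groups A and B, each with its own controls | No |
| Randomization | 64 allocated per month for 4 months | Allocation is not linked to follow-up |
| Timeline | One year of follow-up | Start of the year not given |
| Appendix 1 | Questionnaire before the intervention and 6 months on | No |

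Patients certain to lack an intervention start: 64 + 64 = 128 controls of 256.

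**2. Does the timeline agree with section 6a?** Enrolment from March to June 2023 plus one year gives July 2024, which fits a clock started at enrolment. On the section 6a clock, a patient enrolled in June 2023 whose course fell in July would still be in follow-up when analysis is expected to start. The two are unreconciled, but this is not proof of a contradiction.

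**3. How large could a mismatch be?** The inputs are from section 7a.

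- 1250 contact days per 100 patients is 12.5 days per patient per year. This is the centre-wide 2021 average, not a waiting-list rate.
- Average daily rate: 12.5 / 365.25 = 0.0342 day per day.
- Planned effect: 5% × 12.5 = 0.625 day per patient.

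Assumed scenario: controls are counted from randomisation and intervention patients from a course that starts a mean of *L* days later. Let *w* be the contact rate while waiting, as a fraction of the average, and take the rate at the end of the window to equal the average. Then

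bias (intervention minus control) = *L* × 0.0342 × (1 − *w*)

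The protocol gives neither *L* nor *w*. For *L*, 64 patients a month at 1:1 gives 32 invited, and 32 / 8 = 4 courses. If these run weekly (an assumption), starts on days 0, 7, 14 and 21 average 10.5 days, and starts on days 7, 14, 21 and 28 average 17.5 days. The 14- and 30-day rows extend the range.

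| Mean lag | *w* = 0 | *w* = 0.5 | *w* = 1 |
|---|---|---|---|
| 10.5 days | 0.36 | 0.18 | 0 |
| 14 days | 0.48 | 0.24 | 0 |
| 17.5 days | 0.60 | 0.30 | 0 |
| 30 days | 1.03 | 0.51 | 0 |

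Entries are contact days per patient, against a planned effect of 0.625.

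Break-even lag:

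- *w* = 0: 0.625 / 0.0342 = 18.3 days.
- *w* = 0.5: 0.625 / (0.0342 × 0.5) = 36.5 days.

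In this scenario the later window adds days to the intervention arm and tends to mask a benefit. If contacts taper instead (end-of-window rate 0.5 times the average, starting rate 1 times), the sign reverses: −0.24 day at 14 days and −0.51 day at 30 days.

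**The case against.** The best defence is that a shared calendar date per batch is implied. Allocation runs in monthly batches, each trial group has its own control group, and Appendix 1 applies the intervention's timing to both arms. The Timeline fits such a clock. With a common batch date the bias is zero, and a statistical analysis plan could write the rule down.

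This reading is plausible, but it is inference: no section states it. About four courses a month could also give several start dates within one batch. Nor is this a detail merely left for later, because the protocol does fix time zero for its primary outcome and fixes it on an event that at least half the sample cannot have.

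Several points about size stand:

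- The mismatch scenario appears nowhere in the protocol.
- Only one of the twelve cells exceeds 0.625 day. It needs a 30-day mean lag, which the weekly-course arithmetic does not support, and no contacts while waiting. Zero contact is extreme when usual care stays open and emergency and inpatient contacts count.
- If the SD of 100 days in section 7a is read per patient, the standard error of the difference with 128 per arm is 100 × √(2/128) = 12.5 days, and the largest cell (1.03) is about 8% of that. The units in section 7a are unclear, so this holds only on that reading.
- The self-study offer reduces the number of patients with no possible start. How many remain is unknown.
- The Timeline date is a planning estimate, and the July course is hypothetical.

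**Conclusion.** The concern holds and should be fixed. The primary outcome's time zero cannot be applied to 128 of 256 randomised patients, nor to invited patients who start nothing, and no section supplies a substitute. The control window is undefined rather than shown to differ, and intention-to-treat counting is unsecured rather than shown to fail.

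Confidence is high on the missing definition. The size is conditional on assumed lags and contact rates. It ranges from zero, with a common date or a flat contact rate, to an amount comparable with the planned effect when the lag approaches 18 days and patients have no contacts while waiting. Its direction is not fixed.

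**What to change.** In section 6a, count contact days for 12 months from the date of randomisation for every randomised patient in both arms, whatever the attendance. An acceptable alternative is one index date per monthly batch, set in advance and applied to both arms. This equals randomisation only if the whole batch is randomised on one day.

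Use the same time zero for the 6-month questionnaire and the pharmacy data, and bring the Timeline and Appendix 1 into line.

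The cost is one sentence in 6a and matching wording in those two places. Computer randomisation can supply the dates. The drawback is that a few weeks before the course enter the intervention arm's window and slightly dilute any effect.

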## 11a Blinding

It is not possible in this kind of intra-clinic research to completely blind either patients or therapists. For legal reasons individual treatment plan & course must be described in the electronic patient record. There is also an unavoidable risk that individual patients in the trial groups - or therapists - will talk about eventual Thoughtful program experiences - which may potentially "contaminate" control group patients with Thoughtful knowledge. The size of this risk is probably proportional to perceived benefit. A consequence may be a lowering of effect size.

Moreover the program is freely accessible on the internet - although the Norwegian version is only published shortly before trial start. The reason for this open access approach is that a log-in procedure is considered to be a major obstacle for vulnerable psychiatric patients. From an ethical perspective we also consider that open access to *vital knowledge about life-threatening thoughts* is crucial - for patients and for their primary supportive social network.

---

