## 12a Statistical methods

ANOVA will be used for the statistical analysis.

---

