## Data protection

Anonymous administrative data are extracted for statistical analysis from the authorized University Hospital Patient Record system DIPS ARENA.

Anonymous questionnaire data are recorded and stored in the approved University Hospital Research data center.

Data storage and analysis will apply to EU GDPR standards.

---

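### The wellbeing outcome is a before-to-6-month change compared between arms, but the questionnaire is described as anonymous throughout, with no code linking a patient's two answers or recording the arm

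*Protocol*

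**What the plan says.** Section 6a lists, as a secondary outcome, the average change in score from before to 6 months after "intervention on a 3 item anonymous mental wellbeing questionnaire". Appendix 1 covers both arms: "Both Intervention and control group participants will be asked to answer 3 questions". It describes the answers as anonymous and gives the timing and the tool as follows: "before intervention and 6 months later - via the University Research Department survey program Redcap". Data protection adds: "Anonymous questionnaire data are recorded and stored in the approved University Hospital Research data center". Section 4b places the survey in a database separate from the patient record.

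Section 12a gives the analysis in one line: "ANOVA will be used for the statistical analysis". The Subgroup analyses section expects results to be analysable separately for delivery models A and B.

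The protocol uses the same word elsewhere in a looser sense. Data protection says of the hospital record data: "Anonymous administrative data are extracted for statistical analysis". Section 5 describes attendance at the group course as "just be present - anonymous - listen - and think".

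**The concern.** A change score needs each patient's two answers to be matched, and a randomised comparison needs each answer to carry its arm. The protocol calls the questionnaire anonymous when it is defined, when it is answered and when it is stored. It mentions neither a matching code nor an arm label. As written, the collection rule does not deliver the outcome that section 6a defines.

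This is more than detail that a statistical analysis plan could supply later. Such a plan decides how collected data are analysed; it cannot create a link that was not collected. Record data are different: they are held per patient and can be extracted again with the arm attached.

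The questionnaire is the only listed outcome that patients score themselves, and one of its three items is about suicidal thoughts. The other listed outcomes are service contacts and pharmacy data.

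**Working it through.** The protocol states no standard deviation, effect or power for this outcome, so there is no figure of its own to reproduce. The text settles the main point; the arithmetic shows what is lost.

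**Step 1: what can be computed under each reading.**

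- *No arm label, no pairing (literal reading):* one overall mean per time point. No comparison between arms is possible at any sample size.
- *Arm label, no pairing:* a mean per arm and time point. An average change per arm follows, but not a within-patient change or an adjustment for a patient's own baseline.
- *Arm label and pairing (de-identified reading):* the outcome as section 6a defines it.

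**Step 2: precision with the arm known but no pairing.** Let σ be the standard deviation at one time point (equal at both), n the number per arm, and r the before-after correlation. The protocol does not give r; 0.3 to 0.7 is assumed. The same patients answer at both times. Variances of the arm difference in mean change, in units of σ²/n:

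- True variance, used by a linked analysis: 4(1 − r).
- Variance if the waves are treated as independent: 4.
- Ratio of standard errors: 1/√(1 − r).
- Power, for a difference that linked change detects with 80% power (two-sided 5%, so 1.960 + 0.842 = 2.802): P(Z > 1.96/√(1 − r) − 2.802).
- True type 1 error: 2 × P(Z > 1.96/√(1 − r)).

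For r = 0.5: 1.96/√0.5 = 2.772; 2.772 − 2.802 = −0.030; power = 0.512.

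The alternative of comparing 6-month means only has variance 2, a ratio of 2/[4(1 − r)] to linked change, and power P(Z > 1.96 − 2.802/√ratio).

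| r | SE overstated by | Power, waves treated as independent | True type 1 error | Variance ratio, 6-month means vs linked change | Power, 6-month means |
|---|---|---|---|---|---|
| 0.3 | 1.20 | 68% | 1.9% | 0.71 | 91% |
| 0.5 | 1.41 | 51% | 0.6% | 1.00 | 80% |
| 0.7 | 1.83 | 22% | 0.03% | 1.67 | 58% |

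A simulation with 100 per arm and 20,000 runs gave 0.676, 0.513 and 0.220 for the unlinked analysis, and 0.799, 0.801 and 0.801 for the linked one.

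**Step 3: at the protocol's group size.** Section 7a has 64 patients per group within each delivery model. With all answers returned and standard error √(4(1 − r)/64), linked change detects 0.59, 0.50 or 0.38 SD with 80% power at r = 0.3, 0.5 or 0.7. Two unrelated samples at the two times have standard error √(4/64) = 0.25, and the detectable difference is 2.802 × 0.25 = 0.70 SD.

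**Step 4: a shift in who answers.** Suppose everyone answers at baseline, some do not answer at 6 months, and nobody truly changes. The false arm difference in wave-mean change is then (difference in non-response between arms) × (baseline gap between responders and non-responders). Assume a non-response difference of 0 to 20 percentage points and a gap of 1 to 2 points on the 0-9 scale:

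- 0 × 1 = 0
- 0.10 × 1 = 0.1 points
- 0.20 × 2 = 0.4 points

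Pairing removes this part. It does not remove bias from dropout that depends on the change itself.

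**The case against.** The strongest reply is that the word is used loosely. The record data are also called anonymous, yet they must carry the arm and a 12-month contact count per patient for the primary outcome. Patients sitting together in a course group are called anonymous too. A survey key may exist in data-management papers that are not available here. This stands as a real possibility and limits confidence. It does not close the gap, because the two cases differ: record data are made anonymous on extraction, whereas Appendix 1 has the questionnaire answered anonymously at source.

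Second, an average change needs no pairing if the arm is known. That is correct, and it makes the arm label the indispensable part. But no arm label is described either, and wave means carry the responder-mix problem.

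Third, the figures depend on assumptions. This also stands. The 22% combines the highest assumed correlation with an analysis that treats the waves as independent, which the protocol does not prescribe. The resulting error is conservative and does not create false positives. With the arm known, comparing 6-month means alone matches or beats linked change at r = 0.5 and 0.3, but it is not the change outcome stated.

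Fourth, anonymity may be deliberate because of the suicidal-thoughts item, and changing it might disturb the ethics waiver. The concern about candour is fair. The waiver point is not supported: the Ethics section bases the decision on the project not being a biomedical intervention, not on anonymous data.

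**Conclusion.** The concern holds. The stated way of collecting the questionnaire conflicts with the stated outcome, and the text available contains nothing that reconciles them. On the literal reading the outcome cannot be compared between arms at all. With the arm known but no pairing, the losses are those shown in the working. They rest on assumed correlations of 0.3 to 0.7, the same responders at both waves, waves analysed as independent, and assumed response patterns.

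Confidence is medium, because 'anonymous' may mean only de-identified. The outcome is secondary, and on that reading the primary outcome is not affected. The correction is worth making because it is cheap beforehand and impossible once unlinked answers have been collected.

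**What to change.** Before the first questionnaire goes out, replace 'anonymous' for the questionnaire in section 6a, Appendix 1 and Data protection with wording such as: *pseudonymised under a study code that carries the randomised arm and links both time points; the analyst sees no names*. The code should also identify delivery model A or B, since analysis at that level is expected. Then compare linked change between arms, or the 6-month score adjusted for the patient's own baseline.

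The code could be built into a personal survey link, so patients would not need to log in. Section 11a says of the web program that "a log-in procedure is considered to be a major obstacle for vulnerable psychiatric patients", and the same care is reasonable here.

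If the answers are already coded in this way, it is enough to say so in the three places. The Timeline section expected enrolment from March 2023. If questionnaires have already gone out, the protocol should state what link was in fact collected.

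The cost is survey set-up and a wording change in three sections. The downside is that some patients may answer less candidly, above all on the suicidal-thoughts item.
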